## **ABBREVIATIONS**

Abbreviation	Explanation
AE	Adverse Event
ALC	Absolute Lymphocyte Count
ALT	Alanine aminotransferase
ANC	Absolute Neutrophil Count
AST	Aspartate aminotransferase
CI	Chief Investigator
CNS	Central Nervous System
CR	Complete response
CRUK	Cancer Research UK
CSR	Clinical study report
CT	Computerised tomography
CTAAC	Clinical Trials Awards and Advisory Committee
CTCAE	Common Terminology Criteria for Averse Events
CTS	Clinical Trials Section
CTU	Clinical Trials Unit
CUP	Carcinoma of unknown primary
DCR	Disease Control Rate
DNA	Deoxyribonucleic acid
DSUR	Development Safety Update Report
ECOG	Eastern Cooperative Oncology Group
eCRF	Electronic case report form
EDC	Electronic data capture
EORTC	European Organisation for Research and Treatment of Cancer
EUDRACT	European Clinical Trials Database
ECI	Event of Clinical interest
FFPE	Formalin Fixed Paraffin Embedded
GCP	Good Clinical Practice
GMC	Genomic Medicine Centres
HIV	Human Immunodeficiency Virus
HRA	Health Research Authority
IB	Investigator Brochure
ICD	International Classification of Disease
ICHTB	Imperial College Healthcare NHS Tissue Bank
ICMJE	International Committee of Medical Journal Editors
IEC	Independent Ethics Committee
IUD	Intrauterine Device
IDMC	Independent Data Monitoring Committee
IEC	Independent Ethics Committee
IMP	Investigational Medicinal Product
INR	International normalized ratio
IRB	Institutional Review Board
ir-RECIST	Immune-related
ITIM	Immunoreceptor tyrosine-based inhibition motif

CUPem	C/37/2017	Imperial College London	V7.0; 08.12.2021
-------	-----------	----------------------------	------------------

ITSM	Immunoreceptor tyrosine-based switch motif
IV	Intravenous
JRO	Joint Research Office
LDH	Lactate dehydrogenase
mAb	Monoclonal Antibody
MDT	Multidisciplinary Team
MedDRA	Medical Dictionary for Regulatory Activities
MHRA	Medicines and Healthcare Products Regulatory Agency
MRI	Magnetic resonance imaging
MSI	Microsatellite instability
NCI CTCAE	National Cancer Institute Common Terminology Criteria for Adverse Events
NHSE	National Health Service England
NSAIDs	Non-steroidal anti-inflammatory drugs
OS	Overall Survival
OTC	Over-the-counter
PD	Progressive Disease
PFS	Progression Free Survival
PR	Partial Response
PS	Performance Status
PT	Prothrombin Time
APTT	Activated Partial Thromboplastin Time
QLQ	Quality of Life Quotient
QoL	Quality of Life
Q2W	Every 2 weeks
Q3W	Every 3 weeks
RBC	Red Blood Cell
RECIST	Response Evaluation Criteria in Solid Tumours
SAE	Serious adverse event
SD	Stable disease (RECIST)
SSAR	Suspected Serious Adverse Reaction
SUSAR	Suspected Unexpected Serious Adverse Reaction
TB	Bacillus Tuberculosis
TILs	Tumour-infiltrating lymphocytes
TMG	Trial Management Group
TSC	Trial Steering Committee
ULN	Upper Limit of Normal
WBC	White Blood Cell
WGS	Whole Genome Sequencing

CUPem	C/37/2017	Imperial College London	V7.0; 08.12.2021
-------	-----------	----------------------------	------------------

## **TRIAL SUMMARY**

Abbreviated Title	CUPem
Clinical Indication	A Phase II, Two-Stage, Trial of Pembrolizumab in Cancer of unknown primary
Trial Type	Single Arm, non-randomised; Two-stage; Hypothesis generating
Type of control	None
Route of administration	IV
Trial Blinding	N/A
Treatment Groups	
The study initially opened with a two-cohort design:
 
(i) First Cohort: One or more lines of prior therapy
 
(ii) Second Cohort: First Line untreated CUP patients
 
A substantial amendment in February 2022 has formally closed the second cohort, due to the significant challenges in recruitment caused by the ongoing COVID-19 pandemic as well as associated clinical factors.

Number of trial subjects	Following the closure of the second cohort, the first cohort sample size has been expanded to 31-67 patients. Recruitment will end once 67 patients have been recruited into cohort 1 or at the end of December 2022, whichever is sooner. The precise statistical implications of the eventual recruitment total are detailed (section 8).
Eligibility Criteria	
The Eligibility Criteria are the same as used in the CUP-ONE trial in the UK, please see below.
 
 
• Histologically confirmation of a diagnosis of CUP, with imaging and all diagnostic investigations confirmed as CUP within a CUP MDT.
 
• ECOG Performance Status 0-2
 
• Patients must have disease that is not amenable to potentially curative options such as resection or radical radiotherapy
 
• If patient's disease presentation precludes tumour biopsy (inaccessible or biopsy thought not to be in the patient's best interest), the patient is not study eligible.
 

Estimated recruitment period	2 years
Estimated duration of trial	3.9 years including set up, recruitment, follow up and close down.
Duration of Participation	6-8 months

CUPem	C/37/2017	Imperial College London	V7.0; 08.12.2021
-------	-----------	----------------------------	------------------

## 1 BACKGROUND AND RATIONALE

### 1.1 Introduction

Carcinoma of unknown primary (CUP) is one of the ten most frequent cancer diagnoses and the 5th commonest cause of cancer death in the UK (CRUK mortality data for 2012 (ICD-10 codes C77-80)). Every day in the UK alone, 30 people die from CUP. The ICD-10 (C77-80) coding data show that since 2010, the incidence and mortality have remained static at 9,500 to 10,500 per year. Despite improving diagnostic techniques, only a 13% decline in mortality was achieved in the 6 years between 2006 and 2012. CUP remains a poor prognosis cancer, with median survivals of 8 months from diagnosis and a one year survival probability of 15-35%. Despite this, there are very few randomised clinical treatment studies and therefore little consensus on the optimal treatment regimens. There is no established second-line treatment regimen. The highly metastatic clinical presentation and heterogeneity of CUP at the clinical and pathological level, as well as the possible overlaps with some known primary solid cancers, has also been a practical and intellectual hindrance to the successful classification and treatment strategies.

In 2009/2010 CRUK funded the CUP-ONE Trial (EUDRACT ref 2008-000657-35) which was the first prospective clinico-translational study of cancers of unknown primary with the aim of collecting tissue biopsies in consenting patients and developing (with industry partners) the best rapid molecular classification for carcinomas of unknown primary, initially as a diagnostic validation, and correlation with clinical outcomes. ([name]: CUP-ONE phase II clinico-translational study of Cancers of unknown primary – CRUK project grant C18607/ TRICC grant A7967 & CTAAC grant C18607 Glasgow CTU C18607).

The recruitment in the UK between 2010 and 2014 has led to a successful collaboration between many Cancer Networks and a comprehensive clinical and tissue database of 640 tissue samples. These data are currently being analysed. Preliminary data from the clinical treatment outcomes of the CUP-ONE Trial has been presented (*[name], J. Paul, M.C. Nicolson et al Ann Oncol (2014) 25 (suppl 4): iv397. doi: 10.1093/annonc/mdu345.8*) and demonstrates that two-thirds of patients do not have any treatment offered because of a combination of performance status, lack of efficacy and toxicity of current cytotoxic regimens. Of the treated patients only about a third responds, with a median survival of 8 months for all the treated patients. There is thus a significant unmet need to change the treatment paradigm in CUP.

There has been recent agreement (March 2017) from UK NHSE to prospectively (deep) whole genome sequence 750 genomes from 250 patients within the 100k-genome project. The combination of this and integration with global projects (see below) will allow a more detailed understanding of the biology of CUP, which should apply in a tumour agnostic manner, potentially to all solid cancers that are highly metastatic at presentation. Within the NHS 100k genomes project, there is the ability to link the data to therapeutic interventions including clinical trials.

In addition, ([name]) is a co-applicant in the current Australian Study (**SUPER: Solving Unknown Primary cancer**; [name], and [name], are PI's for the Australian CUP genome sequencing project APP1048193– SUPER 2013 to 2016

CUPem	C/37/2017	Imperial College London	V7.0; 08.12.2021
-------	-----------	----------------------------	------------------

*Funding from Cancer Australia)), which have and are developing tools that might better assess this sensitively in a way that is meaningful to patients with one of its co-primary aims being a comprehensive psychosocial analysis of CUP Patients. We are thus working on better QOL tools for CUP patients.*

#### **1.1.1 Pharmaceutical and Therapeutic Background**

Please also refer to the Investigator's Brochure (IB)/approved labelling for detailed background information on MK-3475. (*Edition 13, February 2017 and any subsequent revisions*).

The importance of intact immune surveillance in controlling outgrowth of neoplastic transformation has been known for decades. Accumulating evidence shows a correlation between tumour-infiltrating lymphocytes (TILs) in cancer tissue and favourable prognosis in various malignancies. In particular, the presence of CD8+ T-cells and the ratio of CD8+ effector T-cells / Fox P3+ regulatory T-cells seem to correlate with improved prognosis and long-term survival in many solid tumours.

The PD-1 receptor-ligand interaction is a major pathway hijacked by tumours to suppress immune control. The normal function of PD-1, expressed on the cell surface of activated T-cells under healthy conditions, is to down-modulate unwanted or excessive immune responses, including autoimmune reactions. PD-1 (encoded by the gene *Pdcd1*) is an Ig superfamily member related to CD28 and CTLA-4 which has been shown to negatively regulate antigen receptor signalling upon engagement of its ligands (PD-L1 and/or PD-L2).

The structure of murine PD-1 has been resolved. PD-1 and family members are type I transmembrane glycoproteins containing an Ig Variable-type (V-type) domain responsible for ligand binding and a cytoplasmic tail which is responsible for the binding of signalling molecules. The cytoplasmic tail of PD-1 contains 2 tyrosine-based signalling motifs, an immune-receptor tyrosine-based inhibition motif (ITIM) and an immune-receptor tyrosine-based switch motif (ITSM). Following T-cell stimulation, PD 1 recruits the tyrosine phosphatases SHP-1 and SHP-2 to the ITSM motif within its cytoplasmic tail, leading to the dephosphorylation of effector molecules such as CD3 $\zeta$ , PKC $\theta$  and ZAP70 which are involved in the CD3 T-cell signalling cascade. The mechanism by which PD-1 down modulates T-cell responses is similar to, but distinct from that of CTLA-4 as both molecules regulate an overlapping set of signalling proteins. PD-1 was shown to be expressed on activated lymphocytes including peripheral CD4+ and CD8+ T-cells, B-cells, T regs and Natural Killer cells. Expression has also been shown during thymic development on CD4-CD8- (double negative) T-cells as well as subsets of macrophages and dendritic cells. The ligands for PD-1 (PD-L1 and PD-L2) are constitutively expressed or can be induced in a variety of cell types, including non-hematopoietic tissues as well as in various tumours.

Both ligands are type I transmembrane receptors containing both IgV- and IgC-like domains in the extracellular region and contain short cytoplasmic regions with no known signalling motifs. Binding of either PD-1 ligand to PD-1 inhibits T-cell activation triggered through the T-cell receptor. PD-L1 is expressed at low levels on various non-hematopoietic tissues, most notably on vascular endothelium, whereas PD-L2 protein is only detectably expressed on antigen-presenting cells found in lymphoid tissue or chronic

CUPem	C/37/2017	Imperial College London	V7.0; 08.12.2021
-------	-----------	----------------------------	------------------

inflammatory environments. PD-L2 is thought to control immune T-cell activation in lymphoid organs, whereas PD-L1 serves to dampen unwarranted T-cell function in peripheral tissues. Although healthy organs express little (if any) PD-L1, a variety of cancers were demonstrated to express abundant levels of this T-cell inhibitor. PD-1 has been suggested to regulate tumour-specific T-cell expansion in subjects with melanoma (MEL). This suggests that the PD-1/PD-L1 pathway plays a critical role in tumour immune evasion and should be considered as an attractive target for therapeutic intervention.

Pembrolizumab is a potent and highly selective humanized monoclonal antibody (mAb) of the IgG4/kappa isotype designed to directly block the interaction between PD-1 and its ligands, PD-L1 and PD-L2. Pembrolizumab has recently been approved in the United States for the treatment of patients with unresectable or metastatic melanoma and disease progression following ipilimumab and, if BRAF V600 mutation positive, a BRAF inhibitor.

### 1.1.2 Preclinical and Clinical Trial Data

Refer also to the pembrolizumab Investigator's Brochure (*Edition 16, 16 June 2018 and any subsequent revisions*) for Preclinical and Clinical data.

## 1.2 Rationale

### 1.2.1 Rationale for the Study and Selected Subject Population

The pathogenesis of CUP is poorly understood. The clinical presentation of a high and poorly differentiated, rapidly progressive tumour burden, without an obvious primary site, leads to an intriguing hypothesis that early transforming malignant and invasive CUP phenotypes, have preferential ability to metastasize rapidly, rather than grow locally initially as in most cancers. One possible explanation of these CUP phenotypes are 'immuno-evasive' leading to unchecked and rampant early spread. This would make the clinical testing of PD-1 inhibitors compelling given their remarkable success in other aggressive phenotypes to date.

The current standard of care for patients, as recently verified in the CUP-ONE trial is ECX (Epirubicin, Cisplatin and Capecitabine (Xeloda®)) chemotherapy administered intravenously and orally in the UK. Each cycle of ECX takes 21 days (3 weeks). However, this standard varies worldwide with alternatives being Gemcitabine and Cisplatin (or Carboplatin) and in the USA – the common first choice option is Paclitaxel with Carboplatin. However, the majority of patients do not get any treatment due to their diminished performance status at presentation (66% of CUP patients are PS2 or more). Overall, the prognosis for CUP patients remains very poor at a median of 6-9 months with conventional chemotherapy, which is poorly tolerated in the PS2 patients, which form the majority of CUP patients. There is thus an urgent need for newer therapeutic approaches in this high area of unmet need. Additionally, CUP is a paradigm for the heterogeneity seen in many solid tumours, when they become highly metastatic, as therapy resistance occurs and become rapidly lethal. Equivalent to ECX is the newer variation EOX (Epirubicin, Oxaliplatin and Capecitabine (Xeloda®)), where the cisplatin is substituted to Oxaliplatin, which is more convenient, shorter, less emetogenic and requires less intravenous hydration.

CUPem	C/37/2017	Imperial College London	V7.0; 08.12.2021
-------	-----------	----------------------------	------------------

### 1.2.2 Rationale for Dose selection/Regimen/Modification

An open-label Phase I trial (Protocol 001) is being conducted to evaluate the safety and clinical activity of single agent MK-3475. The dose escalation portion of this trial evaluated three dose levels, 1 mg/kg, 3 mg/kg, and 10 mg/kg, administered every 2 weeks (Q2W) in subjects with advanced solid tumours. All three dose levels were well tolerated and no dose-limiting toxicities were observed. This first in human study of MK-3475 showed evidence of target engagement and objective evidence of tumour size reduction at all dose levels (1 mg/kg, 3 mg/kg and 10 mg/kg Q2W). No MTD has been identified to date. 10 mg/kg Q2W, the highest dose tested in PN001, will be the dose and schedule utilized in Cohorts A, B, C and D of this protocol to test for initial tumour activity. Recent data from other clinical studies within the MK-3475 program has shown that a lower dose of MK-3475 and a less frequent schedule may be sufficient for target engagement and clinical activity.

PK data analysis of MK-3475 administered Q2W and Q3W showed slow systemic clearance, limited volume of distribution, and a long half-life (refer to IB). Pharmacodynamic data (IL-2 release assay) suggested that peripheral target engagement is durable (>21 days). This early PK and pharmacodynamic data provides scientific rationale for testing a Q2W and Q3W dosing schedule.

A population pharmacokinetic analysis has been performed using serum concentration time data from 476 patients. Within the resulting population PK model, clearance and volume parameters of MK-3475 were found to be dependent on body weight. The relationship between clearance and body weight, with an allometric exponent of 0.59, is within the range observed for other antibodies and would support both body weight normalized dosing or a fixed dose across all body weights. MK-3475 has been found to have a wide therapeutic range based on the melanoma indication. The differences in exposure for a 200 mg fixed dose regimen relative to a 2 mg/kg Q3W body weight based regimen are anticipated to remain well within the established exposure margins of 0.5 – 5.0 for MK-3475 in the melanoma indication. The exposure margins are based on the notion of similar efficacy and safety in melanoma at 10 mg/kg Q3W vs. the proposed dose regimen of 2 mg/kg Q3W (i.e. 5-fold higher dose and exposure). The population PK evaluation revealed that there was no significant impact of tumour burden on exposure. In addition, exposure was similar between the NSCLC and melanoma indications. Therefore, there are no anticipated changes in exposure between different indication settings.

The rationale for further exploration of 2 mg/kg and comparable doses of pembrolizumab in solid tumours is based on: 1) similar efficacy and safety of pembrolizumab when dosed at either 2 mg/kg or 10 mg/kg Q3W in melanoma patients, 2) the flat exposure-response relationships of pembrolizumab for both efficacy and safety in the dose ranges of 2 mg/kg Q3W to 10 mg/kg Q3W, 3) the lack of effect of tumour burden or indication on distribution behaviour of pembrolizumab (as assessed by the population PK model) and 4) the assumption that the dynamics of pembrolizumab target engagement will not vary meaningfully with tumour type.

The choice of the 200 mg Q3W as an appropriate dose for the switch to fixed dosing is based on simulations performed using the population PK model of pembrolizumab

CUPem	C/37/2017	Imperial College London	V7.0; 08.12.2021
-------	-----------	----------------------------	------------------

showing that the fixed dose of 200 mg every 3 weeks will provide exposures that 1) are optimally consistent with those obtained with the 2 mg/kg dose every 3 weeks, 2) will maintain individual patient exposures in the exposure range established in melanoma as associated with maximal efficacy response and 3) will maintain individual patients exposure in the exposure range established in melanoma that are well tolerated and safe.

A fixed dose regimen will simplify the dosing regimen to be more convenient for physicians and to reduce potential for dosing errors. A fixed dosing scheme will also reduce complexity in the logistical chain at treatment facilities and reduce wastage.

### **1.3 Rationale for Endpoints**

#### **1.3.1 Efficacy Endpoint**

There are no established standards of care, consensus, or known benefits to second or more lines of therapy in CUP. Hence a new standard of care needs to be established which is well tolerated and beneficial. Any objective responses or disease control of any significant duration, seen in second line or further are rare so the simple observation of Pembrolizumab (as the test drug here) demonstrating any clinical benefit, where there are no other known treatment options would be an important step in further investigating this strategy in the first line setting.

Initially conceived as a two-cohort study, recruitment had proved challenging for cohort 2 (due to COVID issues). A decision was made in January 2021 for a substantial amendment to lift the recruitment cap in cohort 1 as the minimum effect in  $\geq 1$  participant had been observed and that, as there was no standard of care treatment worldwide for second-line CUP, there would be major interest in understanding meaningful standard of efficacy in cohort 1, as well as in cohort 2 for immunotherapy strategies.

Since this amendment recruitment continued to be difficult, and a new substantial amendment in February 2022 has formally closed the second cohort, due the effect of ongoing COVID-19 pandemic as well as associated clinical factors.

Following the closure of the second cohort, the first cohort sample size is now expanded to a range of 31-67 patients. Recruitment will end once 67 patients have been recruited into cohort 1 or at the end of December 2022, whichever is sooner.. The precise statistical implications of the eventual recruitment total are detailed in full within section 8.

CUPem	C/37/2017	Imperial College London	V7.0; 08.12.2021
-------	-----------	----------------------------	------------------

## 2 OBJECTIVES AND HYPOTHESIS(ES)

### 2.1 Primary Objectives and Hypothesis

#### Objectives:

- Overall response rates by immune-related (irRECIST) and RECIST criteria:
  - Disease Control Rate (DCR), Overall Survival (OS) & Progression Free Survival (PFS).

#### Hypothesis:

Pembrolizumab has Efficacy in CUP:

- as a second-line treatment in terms Response which translates into improved PFS and OS.
- and treatment leads to rapid improvement in QOL in high metastatic disease burden.

### 2.2 Secondary Objectives and Hypotheses

#### Objective:

- Incidence of adverse events up to 8 weeks after the last dose of Pembrolizumab.
- Incidence of adverse events up to 8 weeks after the last dose of Pembrolizumab in Performance Status 2 (PS2) patients.

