### **5.4 End of Study Treatment Visit**

The mandatory Safety Follow-Up Visit should be conducted approximately 30 days after the last dose of trial treatment or before the initiation of a new anti-cancer treatment, whichever comes first. Subjects who are eligible for retreatment with pembrolizumab (Section 5.6) may have up to two safety follow-up visits, one after the Treatment Period and one after the Second Course Phase.

CUPem	C/37/2017	Imperial College London	V7.0; 08.12.2021
-------	-----------	----------------------------	------------------

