**Table 3: Table of Assessments**

Trial Period:	Screening Phase	Treatment Cycles								End of Treatment	Post-Treatment		
Treatment Cycle/Title:	Study Screening	1	2	3	4	To be repeated beyond 8 cycles				Discon	Safety Follow-up	Follow Up Visits	Survival Follow-Up
						5	6	7	8				
Scheduling Window (Days):	-28 to -1		± 3	± 3	± 3	± 3	± 3	± 3	± 3	At time of Discon	30 days post discon	Every 8 weeks post discon	Every 12 weeks
Administrative Procedures													
Pre-screening Visit													
Informed Consent	X												
Inclusion/Exclusion Criteria	X												
Demographics and Medical History	X												
Prior and Concomitant Medication Review	X	X	X	X	X	X	X	X	X	X	X		
Trial Treatment Administration		X	X	X	X	X	X	X	X				
Trial Treatment Compliance		X	X	X	X	X	X	X	X				
Quality of Life Questionnaire (EORTC QLQ-C30)	X					X				X			
Post-study anticancer therapy status											X	X	X
Survival Status		X	X	X	X	X	X	X	X	X	X	X	X
Clinical Procedures/Assessments													
Review Adverse Events	X	X	X	X	X	X	X	X	X	X	X		
Full Physical Examination	X a	X			X				X	X	X		
Directed Physical Examination	X a	X	X	X	X	X	X	X	X	X	X	X	
Vital Signs and Weight	X a	X	X	X	X	X	X	X	X	X	X	X	
ECOG Performance Status	X a	X	X	X	X	X	X	X	X	X	X	X	
Laboratory Procedures/Assessments: analysis performed by LOCAL laboratory													
Pregnancy Test –Serum β-HCG	X b		X c		X c		X c		X c				
PT/INR and aPTT	X d	X e	X e	X e	X e	X e	X e	X e	X e	X	X	X	
CBC with Differential	X d	X e	X e	X e	X e	X e	X e	X e	X e	X	X	X	

CUPem	C/37/2017	Imperial College London	V7.0, 08.12.2021
-------	-----------	----------------------------	------------------

Trial Period:	Screening Phase	Treatment Cycles								End of Treatment	Post-Treatment		
Treatment Cycle/Title:	Study Screening	1	2	3	4	To be repeated beyond 8 cycles				Discon	Safety Follow-up	Follow Up Visits	Survival Follow-Up
						5	6	7	8				
Scheduling Window (Days):	-28 to -1		± 3	± 3	± 3	± 3	± 3	± 3	± 3	At time of Discon	30 days post discon	Every 8 weeks post discon	Every 12 weeks

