#### **6.9.7 Withdrawal from Study**

Withdrawal from the study refers to discontinuation of study treatment and study procedures and can occur for the following reasons:

- Patient decision
- Loss to follow-up
- Death
- Administrative reasons.

CUPem	C/37/2017	Imperial College London	V7.0, 08.12.2021
-------	-----------	----------------------------	------------------

After the end of treatment, each subject will be followed for 30 days for adverse event monitoring (serious adverse events will be collected for 90 days after the end of treatment as described in Section 7. Subjects who discontinue for reasons other than progressive disease will have post-treatment follow-up for disease status until disease progression, initiating a non-study cancer treatment, withdrawing consent or becoming lost to follow-up. Subjects who are discontinued from treatment, but have not progressed at that time, will still be under follow-up for study events of interest (unless lost-to-follow-up or withdrawal of consent). After documented disease progression each subject will be followed by telephone for overall survival until death, withdrawal of consent, or the end of the study, whichever occurs first.

If a patient dies whilst participating in the study a “Statement of Death” eCRF must be completed. The following details will be collected: date of death, whether autopsy performed, whether death was related to the disease under investigation, primary cause of death, secondary cause of death, and any other details.

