### 7.2 Adverse Event recording

AEs will be collected throughout the study, from the point of consent until the Safety Follow Up visit\*; they will be followed up according to local practice until the event has stabilised or resolved, or the follow-up visit, whichever is sooner. Serious Adverse Events (SAEs) will also be recorded throughout the study. See Appendix D for further details.

At the Safety Follow Up visit, any AEs of Grade > 1 which remain unresolved will be followed up by the Investigator until the resolution of the AE to Grade 0-1 or until the beginning of a new anti-neoplastic therapy, whichever occurs first, but without further recording in the eCRF.

\*SAEs, including death that occur within 90 days of the end of treatment or before initiation of a new anti-cancer treatment should also be followed and recorded.

Details to be collected in the eCRF for each AE will include:

- AE description
- Date of onset and date of resolution
- Severity
- Seriousness
- Relationship to study treatment

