5.2 Secondary Efficacy Endpoints

- The incidence of adverse events up to 8 weeks after the last dose of Pembrolizumab will be noted.
- Incidence of adverse events up to 8 weeks after the last dose of Pembrolizumab in Performance Status 2 (PS2) patients.

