6.4 Secondary Efficacy Analysis

Incidence of adverse events up to 8 weeks after the last dose of Pembrolizumab will be measured.

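### The secondary endpoint counts adverse events to 8 weeks after the last dose, but routine recording of non-serious events ends at the safety visit at about 30 days, so later ones are under-ascertained

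*Protocol*

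**What the plan says.** **The endpoint.** Protocol 2.2 lists two secondary objectives. The first is "Incidence of adverse events up to 8 weeks after the last dose of Pembrolizumab"; the second is the same quantity in PS2 patients. Protocol 8.1.1 repeats both. SAP 2.2 carries them over, SAP 5.2 states "The incidence of adverse events up to 8 weeks after the last dose of Pembrolizumab will be noted" and adds the PS2 version, and SAP 6.4 states "Incidence of adverse events up to 8 weeks after the last dose of Pembrolizumab will be measured" without separate mention of PS2. None of these places limits the count by seriousness or severity.

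**Collection of AEs in general.** Protocol 7.2 says "AEs will be collected throughout the study, from the point of consent until the Safety Follow Up visit". Protocol 5.4 places that visit "approximately 30 days after the last dose of trial treatment or before the initiation of a new anti-cancer treatment, whichever comes first". Protocol 6.9.7 says that, once treatment has ended, "each subject will be followed for 30 days for adverse event monitoring". In Table 3 of the protocol, and in the matching SAP schedule, the AE review row is marked from screening to the safety follow-up. It is blank for the 8-weekly follow-up visits and for survival follow-up. Under protocol 7.2, events above Grade 1 still open at the safety visit are followed clinically but no longer entered in the eCRF.

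**Exceptions.** SAEs are collected to 90 days after the end of treatment or until new anti-cancer therapy (protocol 6.9.7 and 7.2; SAP 5.3). ECIs are reported to 90 days after treatment stops, or to 30 days if new therapy starts (protocol 7.10).

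**The anchor.** Protocol 5.4 dates the safety visit from the last dose. Table 3 dates it "30 days post discon", and the SAP 6.1 flow chart also counts its 30 days from discontinuation.

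**The concern.** The reporting window is longer than the routine recording window. If the SAP is followed exactly, a table headed as 8-week incidence will contain non-serious events only up to the safety visit. SAP 6.8 allows no imputation, so an event that nobody was scheduled to ask about is counted as absent. The error can only lower the incidence, which is the direction that favours the hypothesis in protocol 2.2 that pembrolizumab is better tolerated than chemotherapy.

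Late events are foreseeable on the protocol's own account: section 3.3.1 says that AEs may appear months after treatment has stopped. AE incidence is also the only secondary endpoint, and it has to be read separately in PS2 patients. Because the visit moves with new therapy and has two possible anchors, the length of observation also differs between patients according to why and when they stopped.

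**Working it through.** The plan states no AE rate, sample size or power for this endpoint, so there is no figure to reproduce. The check compares windows.

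**Inputs**
- Endpoint window: 8 weeks after the last dose (protocol 2.2; SAP 5.2, 6.4), so 8 × 7 = 56 days.
- Routine AE recording: to the safety visit, 30 days after the last dose (protocol 5.4) or after discontinuation (Table 3; SAP 6.1).
- SAEs and ECIs: 90 days, with the new-therapy limits above.
- Cycle length: 21 days (protocol 5.8).
- Longest toxicity hold before discontinuation for most entries in protocol Table 2: 12 weeks, so 12 × 7 = 84 days.

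**Formula.** Let *k* be the number of days from last dose to the date from which the visit is counted. Recording ends on day *k* + 30, and the gap is max(0, 56 − (*k* + 30)).

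| Case | Recording ends | Gap | Share of 56 days |
|---|---|---|---|
| Visit dated from last dose, *k* = 0 | day 30 | 26 days | 26/56 = 46% |
| Visit dated from discontinuation, declared at the next 21-day visit (assumption), *k* = 21 | day 51 | 5 days | 5/56 = 9% |
| Discontinuation after an 84-day hold, *k* = 84 | day 114 | 0 days | 0% |
| Visit brought forward to day *d* < 30 by new therapy | day *d* | 56 − *d*, more than 26 days | above 46% |

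**SAEs and ECIs.** Since 90 > 56, neither has a gap unless new therapy starts before day 56. In that case SAE collection stops at the new therapy and ECI collection stops at day 30.

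**Illustration of lost events.** Assume a flat event rate over the 56 days and that 60% to 90% of events are non-serious. Neither assumption comes from the documents, and ECIs are ignored.
- With the 26-day gap, the share of post-dose events not recorded is 26/56 × 0.60 = 28% to 26/56 × 0.90 = 42%.
- With the 5-day gap, it is 5/56 × 0.60 = 5% to 5/56 × 0.90 = 8%.

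These are shares of post-dose events. They are not shares of all events in the endpoint, which also covers the treatment period, and not shares of patients.

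**Do other passages close the gap?** Protocol 5.9.7 speaks of AE monitoring throughout the study but refers to section 7 for detail, and section 7 contains the cut-off. The 8-weekly follow-up visits exist only for patients who stop for reasons other than progression (protocol 5.5), and AE review is not marked for them. After confirmed progression or new therapy, the only contact is a telephone call every 12 weeks for survival status (protocol 5.5.1).

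**The case against.** The best defence is that the parts of the endpoint that matter most are collected. All on-treatment AEs are captured, all AEs are captured to the safety visit, and SAEs and ECIs run past day 56 for patients who start no new therapy. The analysis is a descriptive table in a single arm with no AE threshold or decision rule. A patient-level proportion with any AE may hardly change, because most patients who would count may already have had an event on treatment. All of this stands, and it limits the weight of the point. It does not reconcile 8 weeks with 30 days.

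Four stronger readings are tempting, and the documents do not support them.
- *The endpoint cannot be measured.* A reader might infer this from the mismatch. Most of it can be; what is incomplete is the count of non-serious, non-ECI events first arising after the safety visit.
- *Such events are never recorded.* Protocol 7.3 requires clinically important laboratory abnormalities during the study to be recorded as AEs. The 8-weekly follow-up visits include blood counts, coagulation and thyroid tests, so these abnormalities have a recording route in the patients who attend.
- *Every patient loses at least 26 days.* That holds only if the visit falls on or before day 30 after the last dose. Protocol 5.4 calls the interval approximate, and Table 3 and SAP 6.1 date it from discontinuation.
- *One AE question at an existing 8-week contact would cure it.* Patients with confirmed progression or on new therapy have no such contact, and the follow-up visits are dated from discontinuation, not from the last dose.

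**Conclusion.** The inconsistency is real. The 8-week all-AE incidence, overall and in PS2 patients, is incompletely ascertained and biased downward for events that are neither serious nor ECIs and begin after the safety visit. The unobserved stretch is 26 of 56 post-dose days (46%) if the visit is 30 days after the last dose. It is about 5 days (9%) if the visit is counted from a discontinuation declared at the next 21-day visit, which is an assumption. It is nil after a long hold, and more than 26 days if new therapy brings the visit forward. How many events this represents cannot be derived from the documents. No primary endpoint, sample size or stopping rule is affected. It should still be settled before analysis, because non-serious events that were not recorded at the time cannot be recovered reliably afterwards.

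**What to change.** 1. In protocol 2.2 and 8.1.1 and SAP 2.2, 5.2 and 6.4, restate the endpoint as two quantities: (a) all AEs from first dose to the safety visit; (b) SAEs and ECIs to their existing limits, including the new-therapy limits. Report the two separately, each overall and for PS2 patients, and name PS2 in SAP 6.4.
2. Reconcile the date from which the safety visit is counted (last dose in protocol 5.4; discontinuation in Table 3 and SAP 6.1) and use one anchor throughout.
3. State the window in the AE and SAE table titles in SAP 6.11, which currently give none.

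This is wording only. It changes no visit, treatment or sample size. Its cost is the usual amendment route for the protocol text: ethics approval where required (protocol 9.3.2) and HRA and site notification (9.5). Keeping a true 8-week window for all AEs would instead need a new AE contact for every patient, including those in survival follow-up, and would help only patients not yet past that point.
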